In summary, there is a great-unmet need for non-invasive treatments for chronic knee pain due to OA. In this proposal, we will test whether tDCS applied in conjunction with TUS is effective in treating chronic knee pain from OA.

Sponsors

This study is to be funded by the National Institutes of Health (Highland Instruments SBIR). Highland Instruments is a company focused on developing neurostimulation technologies for treatment of neural pathologies.

II. SPECIFIC AIMS

In this study, we aim to assess the effects of tDCS in combination with TUS for the treatment of pain and functional limitations in subjects with OA of the knee. We will explore *Aim 1 Sub-aims 1.1- 1.4* with a parallel design (active tDCS+ active TUS (n=32), and sham tDCS+sham TUS (n=32)). The specific aims of this experiment are as follows:

Aim 1: Assess the preliminary therapeutic effects of tDCS in conjunction with TUS in chronic OA knee pain.

Sub Aim 1.1: Safety of tDCS+TUS in subjects with OA of the knee.

We hypothesize that tDCS in conjunction with TUS can be applied safely in OA subjects. To test this we will implement a comprehensive battery of safety and neurological tests in OA subjects following fixed doses of tDCS in conjunction with TUS provided over [REDACTED] [REDACTED] for 10 days, 20 minutes/day. These assessments include EEG recordings, Visual Analog Mood Scale (VAMS), Mini Mental Status Exam (MMSE), 4-Choice Reaction Time, adverse events (AE) questionnaire and Neurological and physical examinations. We will compare active tDCS+ active TUS (n=32), and sham tDCS+sham TUS (n=32), inactive transducers. Follow-up evaluations will continue, while no further treatment is given, for 8 weeks (at 1, 2, 4, and 8 weeks) after the last stimulation.

Sub Aim 1.2 Effects of tDCS+TUS in pain perception in subjects with OA of the knee.

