Visual Analog Mood Scale (VAMS): This is a self-assessment scale in which subjects rate their own emotions, including anxiety, depression, stress, and sleepiness along a 100 mm line.

Mini Mental Status Exam (MMSE): This is a sensitive, valid and reliable 30-point questionnaire that is used extensively in clinical and research settings to measure cognitive impairment. This instrument will be used as a brief screening of cognitive abilities. The MMSE will be administered at the baseline evaluation and every subsequent visit.

4-Choice Reaction Time: Patients will be seated in front of a computer screen placed at eye level. One of four possible circles, each 4 cm in diameter, will be presented horizontally spaced on the screen and aligned above the appropriate response keys. The stimuli will be generated and response times recorded using Superlab pro v2.0 software (Cedrus Corporation, San Pedro, Ca). The patients have to push the key aligned with the circle that appeared using only the index finger of the dominant hand. The circle will not disappear until the correct button is pushed. The time between the appearance of the circle and the push of the correct response key will be defined as the choice reaction time. The 4-choice reaction time will be administered at the baseline evaluation and every subsequent visit.

Adverse Effects Questionnaire: At each session after stimulation begins, subjects will complete a questionnaire to evaluate potential adverse effects of stimulation (headache, neck pain, mood alterations, and seizures) on a 5-point scale. The scale will also be administered at the follow-up. The subjects will be asked whether they have experienced any side effects in an open-ended manner and they will then be specifically asked about headache, neck pain, scalp pain, scalp burns, tingling, skin redness, sleepiness, trouble concentrating, and acute mood change. If any side effects are reported, the degree of relatedness to the intervention will be assessed.

We will be investigating adverse effects using open-ended questions. An AE can be any unfavorable and unintended sign, symptom, or disease temporally associated with the use of a treatment, whether or not considered related to the product.

Examples of AEs are as follows:

- Subjective symptoms offered by or elicited from the subject
- Objective signs observed by the Investigator or other study personnel

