All analyses will be conducted according to the principle of intention-to-treat (using regression-based single imputation method). Intention-to-treat (ITT) population will include all randomized subjects. We will also perform an additional sensitivity analysis in which we will use the method of multiple imputation. The primary outcomes will be pain changes as indexed by VAS scores, biomechanical function changes as indexed with the motion analysis suite (i.e., our biomechanical data acquisition and analysis system), and QOL changes. Differences between the groups will be tested using Student's t-test, and additionally we will adjust for important baseline variables and test the time effect in general mixed longitudinal models. This model will be used for the primary and secondary outcomes (dependent variable (one model for each variable): VAS scores, biomechanical function changes as indexed with the motion analysis suite, and QOL changes, and independent variables will be treatment group and time of assessment (we will also adjust for baseline pain levels in this model)). Secondary analyses will be conducted in an exploratory manner (no correction for multiple comparisons). We will also conduct an EEG analysis to correlate EEG data with pain measures. Similar analysis will be conducted for the adverse effects measuring continuous outcome and for the categorical outcomes we will use Fisher's exact test. In both cases, for safety analysis we will use uncorrected p-value to increase the likelihood of detecting detrimental adverse effects.

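### Continuous safety outcomes fall under the efficacy imputation rule with no exception, so harm in subjects who stop because of it can be diluted or removed from the active-versus-sham comparison

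*Combined protocol and SAP*

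**What the plan says.** Section VII (Biostatistical Analysis) sets one general rule: "All analyses will be conducted according to the principle of intention-to-treat (using regression-based single imputation method". The population is equally general: "Intention-to-treat (ITT) population will include all randomized subjects". For missing data it adds one check: "We will also perform an additional sensitivity analysis in which we will use the method of multiple imputation". The same paragraph then turns to safety: "Similar analysis will be conducted for the adverse effects measuring continuous outcome and for the categorical outcomes we will use Fisher's exact test". It explains why no multiplicity correction is applied: "for safety analysis we will use uncorrected p-value to increase the likelihood of detecting detrimental adverse effects".

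The text supplied has no safety population, no missing-data rule for safety and no list of imputation predictors. It also does not say whether a subject who stops stimulation still attends later visits.

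Safety is the subject of Section II, Sub Aim 1.1: "These assessments include EEG recordings, Visual Analog Mood Scale (VAMS), Mini Mental Status Exam (MMSE), 4-Choice Reaction Time, adverse events (AE) questionnaire", together with neurological and physical examinations. Under the visit schedule in Section VI, the mood scale, MMSE, reaction time and adverse-effects questionnaire are completed after all 10 stimulation sessions and at the 4 follow-up visits. The questionnaire description in Section VI confirms this: "At each session after stimulation begins, subjects will complete a questionnaire to evaluate potential adverse effects of stimulation", and "The scale will also be administered at the follow-up".

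**The concern.** In a safety analysis, withdrawal carries information. A subject who stops because of slowed reactions, mood change or scalp pain may leave poor values up to the stop and nothing after it. A regression fitted to the subjects still observed then supplies the later values. Those subjects mostly did not have the harm, so the prediction is too favourable. If such stops are more common on active stimulation, the comparison moves toward no difference, which is the result that favours the safety hypothesis of Sub Aim 1.1. The plan gives up multiplicity correction to gain sensitivity to harm, and the imputation rule works in the opposite direction. Multiple imputation does not cure this if it too assumes that data are missing at random.

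**Working it through.** **No figure to reproduce.** The plan states no dropout rate, no imputation model and no expected size of harm. The only design input is 32 subjects per group (Section VII). Everything else here is an assumption.

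**Assumptions.** Scores are standardised to SD 1, and any two visits on the same subject have correlation r = 0.6. In the active arm, *k* of 32 subjects have a harm of *D* SD, stop, and have no Day 10 value. No sham subject stops.

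**True difference at Day 10:** *k*/32 × *D*.

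**Imputation from baseline and arm.** Neither predictor carries the harm, so the expected difference is 0.

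**Imputation from baseline, arm and the subject's own last value, which already shows the harm.** With *m* equally correlated earlier values, each has coefficient r / (1 + (*m* − 1)r). For *m* = 2 this is 0.6 / 1.6 = 0.375, so 37.5% of the difference is kept.

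| *k*, *D* | True | Baseline + arm | With last value |
|---|---|---|---|
| 3, 1.5 SD | 3/32 × 1.5 = 0.14 | 0 | 0.14 × 0.375 = 0.05 |
| 4, 2 SD | 4/32 × 2 = 0.25 | 0 | 0.25 × 0.375 = 0.09 |
| 8, 3 SD | 8/32 × 3 = 0.75 | 0 | 0.75 × 0.375 = 0.28 |

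Simulation with 32 per arm agrees with these values to within about 0.02 SD. The loss is therefore about 60% to 100%, depending on a model that the plan does not state.

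**Effect on detection (simulated two-sided 5% t-test).** For 4 of 32 with 2 SD, detection is about 13% with complete data and 6% to 7% after imputation. For 8 of 32 with 3 SD it is roughly 60% with complete data, 6% to 8% with baseline and arm, and 18% to 20% with the last value.

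**Categorical events.** An event recorded before the stop is observed, so imputation does not change it. Two-sided Fisher's exact test gives p = 0.024 for 6/32 versus 0/32 and p = 0.005 for 8/32 versus 0/32, whether or not those subjects later stop.

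**Candidate remedies.**

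- *Observed cases at Day 10 only.* The harmed subjects drop out of the comparison, and the simulated difference is again about 0.
- *Worst post-baseline value.* A completer has 10 + 4 = 14 reaction-time measurements; a subject who stops after session 3 has 3. The expected maximum of independent normal noise is 1.70 SD for 14 values and 0.85 SD for 3. With no harm at all, and within-subject noise of √0.4 = 0.63 SD, 3 early stops shift the active mean by 3/32 × 0.85 × 0.63 = 0.05 SD in the favourable direction. Eight stops shift it by 8/32 × 0.85 × 0.63 = 0.13 SD.
- *Mixed model on all observed sessions.* With baseline and three harmed sessions observed, the same formula gives 3 × 0.6 / (1 + 3 × 0.6) = 1.8 / 2.8 = 64% of the Day 10 difference kept. This is better, but not complete.

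**The case against.** The strongest reply is that the loss may make little practical difference. At a true difference of 0.14 SD, 32 per arm gives only about 8.5% power, so complete data would rarely show the harm either. That stands for mild cases. It does not stand for the larger ones, and even a small difference should not be removed by rule from the reported estimate.

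Second, the imputation model is unstated, and the planned longitudinal model may carry over to safety, in which case early poor values enter as data. This also stands: the effect is dilution in some versions and removal in others.

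Third, no text says that a subject who stops stimulation misses later visits. If such subjects continue to attend, the problem shrinks.

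A reader might go further and infer that categorical adverse effects are masked too: 6 versus 0 events (p = 0.024) becoming 3 versus 0 (p = 0.24) once three stoppers are imputed as event-free. The documents do not support this. They name no single visit for analysing adverse effects and no event-free imputation, and they collect effects at every session.

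A reader might also infer that never-stimulated subjects would fill the safety denominator with invented values. Section VI places randomization immediately before the first session, so such subjects should be few.

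Nor would the safety conclusion rest on predictions alone. Section VI also has adverse events assessed for seriousness, severity, duration and causality, and refers to a Medical Monitor and an IMC.

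**Conclusion.** The point holds for continuous safety outcomes: the mood scale, MMSE, reaction time and rated adverse-effect scores. Read as written, the general rule covers them, and it can only work against the stated aim when subjects stop because of harm and their later values are missing. In the illustration, 60% to nearly 100% of the Day 10 difference is lost. This rests on an assumed correlation of 0.6, assumed numbers and sizes of harm, stops in the active arm only, and no data after the stop. The documents supply none of these, so the direction is firm and the size is not. The point does not extend to categorical adverse effects recorded before a stop. It should be corrected because a stated rule conflicts with a stated aim in the same paragraph.

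**What to change.** Amend Section VII as follows:

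1. Exempt safety outcomes from imputation.
2. Analyse safety in subjects who received at least one stimulation session.
3. Define each categorical adverse effect as any occurrence at any session or follow-up visit, compared by Fisher's exact test.
4. Analyse continuous safety measures with the longitudinal mixed model already planned, on all observed post-session values. Do not use a single late visit or an unadjusted worst value.
5. Add discontinuation of stimulation because of an adverse effect as a categorical outcome, compared by arm with Fisher's exact test.
6. Add a sensitivity analysis that assigns prespecified unfavourable values after a stop for harm.

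Items 5 and 6 are needed because the mixed model alone does not fully recover harm after a stop. The cost is a few lines of text. Nearly all the data are already collected; the reason for stopping must also be recorded. Any never-stimulated subjects leave the safety denominator.

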For planning sample size calculation for this study, we utilized the OARSI recommendations for the management of knee OA. In this recommendation [84], a panel of experts reviewed evidence for the most commonly used pharmacological and non-pharmacological interventions for OA pain, giving effect sizes for all these interventions. Examples of non-pharmacological interventions are: education, physical therapy, aerobic exercise, knee brace, footwear, thermal modalities, TENS and acupuncture. Examples of pharmacological treatments are: acetaminophen, NSAIDs, injections with corticosteroids and treatment with glucosamine. In this review, effect sizes vary from 0.06 to 0.72. In fact the largest effect size was shown with injection of corticosteroids. Based on these effect sizes and the effect size we found in our pilot data (1.4), we set the effect size for our sample size calculation considering a effect size smaller or equal than our pilot data and larger than the

larger effect size from this meta-analysis (0.72) [84]. For this particular protocol, we plan a sample size of 64 participants. We considered the same sample per group as four times the subjects in Phase 1: 32 subjects per group. This will be enough to detect a difference in effect size of 0.9 and thus an effect size that is superior than other treatments used in OA according to a large guideline on OA management [84], though we expect a larger effect size for pain. However it is important to be able to detect significance with smaller effect sizes in the Phase 2 work, as some of the neurophysiological outcomes require additional power. Note that the main aim here would still be the comparison of active ESSstim vs. sham ESSstim.

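### The safety analysis states no basis for concluding that the combination is safe: Fisher's exact test at 32 per arm usually misses moderate excesses of harm, and no interval or margin is planned

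*Combined protocol and SAP*

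**What the plan says.** Section II, Sub Aim 1.1, states the safety hypothesis: "We hypothesize that tDCS in conjunction with TUS can be applied safely in OA subjects". It is to be examined with a battery of safety assessments compared between 32 active and 32 sham subjects.

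The last paragraph of section VII gives the analysis. For continuous safety measures, "Similar analysis will be conducted for the adverse effects measuring continuous outcome", which refers back to the t-test and mixed models used for efficacy. For the rest, "for the categorical outcomes we will use Fisher's exact test". On multiplicity it says that "for safety analysis we will use uncorrected p-value to increase the likelihood of detecting detrimental adverse effects".

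The sample size was set for efficacy: "We considered the same sample per group as four times the subjects in Phase 1: 32 subjects per group". The only detectable difference given is for efficacy: "This will be enough to detect a difference in effect size of 0.9". The documents give no alpha, sidedness, expected adverse-effect rate, safety power, safety margin, acceptable rate or confidence interval for safety.

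**The concern.** Two parts of the plan do not fit together.

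First, section VII sets sensitivity to harm as the aim of its safety testing. Fisher's exact test conditions on the total number of events. With 32 per arm and uncommon events, few tables are possible and the test uses only part of its nominal error rate, which lowers its sensitivity.

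Second, Sub Aim 1.1 hypothesises safety, but the only formal between-arm inference is a test of difference. A p-value above the threshold is the result that agrees with the hypothesis. It is also the result that low power tends to produce. Without an interval or margin, the analysis cannot separate evidence of little or no excess from too little information.

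At stake is what can be said under Sub Aim 1.1. The efficacy comparison is not affected.

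**Working it through.** **Inputs from the documents:** 32 per arm, 1:1 allocation, all randomized subjects analysed (section VI, Randomization; section VII).

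**Assumptions, because the documents are silent:** two-sided 0.05; each subject counted once, yes or no, for a given adverse effect; event rates as shown.

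**The plan's own figure.** For efficacy, power at effect size 0.9 is about Φ(0.9 × √(32/2) − 1.96) = Φ(3.60 − 1.96) = Φ(1.64) = 95%. So 32 per arm is ample for 0.9. There is no safety figure to reproduce.

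**Fisher's rejection region when sham has no events.** With x active events and 0 sham events, two-sided p = 2 × C(32,x)/C(64,x).
- x = 5: 2 × 201,376/7,624,512 = 0.053, not significant.
- x = 6: 2 × 906,192/74,974,368 = 0.024, significant.

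So 6 v 0 is needed. With one sham event, 8 active events are needed (8 v 1: p = 0.026; 7 v 1: p = 0.053).

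**True size.** Enumerate all 33 × 33 outcomes and add Bin(a; 32, π) × Bin(b; 32, π) over the tables rejected. Boschloo's p-value is the maximum, over the common rate π, of the probability of a Fisher p-value no larger than the one observed.

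| Common rate | Fisher | Boschloo |
|---|---|---|
| 5% | 0.2% | 0.8% |
| 10% | 1.1% | 2.5% |
| 20% | 2.4% | 3.9% |
| Maximum over all rates | 3.3% | 4.7% |

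Fisher rejects 640 tables. Boschloo rejects the same 640 and 32 more, including 5 v 0 (p = 0.033) and 7 v 1 (p = 0.033).

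**Power.** The same sum with different rates in the two arms. With a sham rate of 0% it reduces to P(X ≥ 6) for Fisher and P(X ≥ 5) for Boschloo, X ~ Bin(32, active rate).

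| Sham v active | Fisher | Boschloo |
|---|---|---|
| 0% v 10% | 9% | 21% |
| 0% v 15% | 35% | 54% |
| 5% v 20% | 28% | 37% |
| 10% v 30% | 41% | 49% |
| 5% v 30% | 68% | 75% |
| 10% v 40% | 75% | 80% |

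**Test or sample size?** For 5% v 20%, changing the test adds 37 − 28 = 9 points. By the normal approximation, 80% power there needs about 76 per arm. Most of the shortfall is the sample size.

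**What intervals would show.**
- 0/32 events: upper two-sided 95% limit = 1 − 0.025^(1/32) = 10.9%.
- 3/32 v 3/32: Fisher p = 1.0, but the Newcombe 95% interval for the risk difference is about −16 to +16 points.
- 5/32 v 0/32: Fisher p = 0.053, but the Newcombe interval is +1.8 to +31.8 points.

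**The case against.** The strongest reply has five parts.

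**The error rates rest on assumptions.** This stands. A reader might take 0.2% to 2.4% as a fixed property of the planned test. It holds only for two-sided 0.05 and common rates of 5% to 20%. If effects such as tingling or redness occur in 30% to 50% of subjects, the size is 2.8% to 3.3%.

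**Sidedness matters.** Section VII is concerned with detrimental effects, which could mean a one-sided test. One-sided Fisher at 0.05 gives p = 0.026 for 5 v 0 and power of 21%, 54% and 53% for 0% v 10%, 0% v 15% and 10% v 30%. That equals or exceeds two-sided Boschloo, although it allows up to 5% error in the harmful direction alone. So the documents do not establish that 5 v 0 would be reported as non-significant. The missing alpha and sidedness are part of the problem.

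**Harm detection does not rest on this test.** Section VI provides for relatedness assessment of reported side effects and for review of seriousness, severity and duration, and it mentions a Medical Monitor and an IMC. Continuous safety measures do not use Fisher's test. A reader might infer that real harms will go unnoticed; the documents do not support that, and power is 68% to 75% for the larger excesses in the table. These safeguards work case by case, however, and give no between-arm estimate for Sub Aim 1.1.

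**Nobody says that non-significance will be read as safety.** Correct. A reader might infer it because no other decision rule is given, but no passage states it, and Aim 1 is described as preliminary. What stands is that a rule is missing.

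**Boschloo's test may not fit the data.** The questionnaire in section VI uses a 5-point scale. Boschloo's test applies only to yes/no tables, and collapsing the grades loses information. The change of test should therefore be limited to yes/no outcomes.

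Dropping multiplicity correction does raise sensitivity across the nine symptoms asked about. It does not make up for the small sample or the discreteness of the test.

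**Conclusion.** The concern holds in a conditional form. Under the stated assumptions, Fisher's test uses well under half of its nominal 5% at common rates of 5% and 10% and about half at 20%, and never more than 3.3%. Power for the moderate excesses examined is 9% to 41%. The main cause is 32 per arm; the choice of test is a secondary cause that works against the plan's own aim. The more important gap is that Sub Aim 1.1 has no interval, margin or acceptable rate behind it, so a non-significant test cannot by itself support the hypothesis of safety. That conclusion does not depend on the assumed event rates. The change should be made, but the efficacy result does not depend on it.

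**What to change.** Amend section VII in two places.

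1. Base the Sub Aim 1.1 conclusion on estimates: the active-minus-sham risk difference with a 95% confidence interval for each adverse effect, and mean differences with 95% intervals for MMSE, VAMS and reaction time. State that non-significance will not be read as safety, and that 0/32 events excludes only rates above about 11%.
2. For yes/no adverse-effect outcomes, with each subject counted once per effect, replace Fisher's test by Boschloo's unconditional exact test, and state alpha and sidedness. Continue to report the 5-point severity grades.

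The cost is a few sentences and software that offers the unconditional test. No subjects or assessments are added. The downside is slightly more chance positives (still below 5% per test at two-sided 0.05) and a more modest safety statement. Power stays limited: changing the test does not remove the effect of 32 per arm, which is why the intervals should carry the conclusion.
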